Potential Adverse Events and Adverse Device Effects associated with any large bore intervention, including the use of the MANTA VCD, include but are not limited to:

- Failed hemostasis.
- Damage to the superficial femoral artery.
- Local trauma to the femoral artery wall.
- Damage to the inguinal ligament, causing retroperitoneal bleeding.
- Accidental positioning of collagen plug within the femoral artery, leading to ischemia or stenosis.
- Other access site complications leading to bleeding, hematoma, pseudoaneurysm, etc., possibly requiring blood transfusion and/or surgical intervention.

9.3. *Relationship of Adverse Event to Device*

Each reported AE will be assessed by the Investigator for its primary suspected relationship to the closure device.

- MANTA Study AEs related to the MANTA closure device and/or its deployment (in total, the closure procedure) are considered Device-Related AEs.

The causal relationship of an AE to the device will be classified as follows:

- Not Related: An AE which cannot be attributed to the MANTA device or initial study procedure.
- Possible: The clinical event occurs within a reasonable time sequence to device and there is some evidence to “possibly” suggest a causal relationship. However, the influence of other factors such as underlying disease, concomitant medications, or concurrent treatment may have contributed to the event
- Probable: The temporal sequence between the device use and the event is such that the relationship is likely or patient’s condition or concomitant therapy could have caused the AE
- Definite: The clinical event occurs in a plausible time relationship to device and cannot be explained by any concurrent disease or other devices, drugs or chemicals

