9.5. Reporting of Adverse Events

9.5.1 SAE and AE Reporting to Sponsor

Safety Surveillance within this registry and the safety reporting performed by both the investigator and Sponsor starts from the point of attempted MANTA placement and onward. The safety surveillance and the safety reporting will continue until the last visit has been performed, the subject is deceased. The subject/investigator concludes their participation in the study or the subject/investigator withdraws the subject from the study. All device-related SAEs from the point of attempted MANTA placement and onward will be reported to the Sponsor within 24 hours of the Investigator’s first knowledge of the event. Suspected SAEs also should be reported. Investigators should also report AEs or SAEs that are known to be unrelated to the device on eCRF.

The Investigator will forward information about a device-related SAE promptly and complete the AE and SAE report forms provided by the Sponsor, even if the information is incomplete or it is obvious that more data will be needed to form any conclusions. Additional information regarding the SAE will be recorded on the follow-up SAE form and forwarded to the Sponsor.

All MANTA device-related AEs, and AE’s associated with non-MANTA access sites, and additional outcomes not associated with MANTA device should be reported on the eCRF as soon as practicably possible. Such AEs will be recorded by their final medical diagnosis and not by each separate symptom. All AEs categorized by the Investigator as associated with MANTA leg and categorized by the Investigator as possibly, probably or definitely device-related, will be reviewed by the Clinical Events Committee for a final adjudication. The information for the event will include the date of onset and resolution, the action taken, the intervention/treatment and how the subject recovered with or without sequelae. In case of death, the relationship of death to the MANTA device and/or the study procedure will be well documented. The date on

which subject expired, what attempts were made to treat the event that led to death, the performance and functioning of the device during the event will be noted.

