### 3 Clinical Events Committee

An independent Clinical Events Committee (CEC) will be established for this study. The CEC will include members qualified to review adverse event data for this study. During the CEC review, a designated CEC member is responsible for reviewing the documentation for events that occurred in their country. If complex events emerge, the designated CEC member can ask the CEC Chair to convene a conference call to discuss the specific event(s). The CEC will be established and operate according to a charter defined prior to the initiation of the trial. The CEC will review individual adverse events that meet the following criteria:

- AEs that are considered by the investigator to be definitely, probably or possibly device related will be adjudicated by CEC parallel to enrollment. Additionally, outcomes not associated with the MANTA device may also be adjudicated by CEC.

The primary responsibilities of the CEC over the course of the study are to review and refine serious adverse event definitions, and to review and adjudicate serious adverse events.

The CEC will determine if each reviewed adverse event meets the definition of a VARC-2 Major femoral vascular complication or a VARC-2 Minor femoral vascular complication or neither definition. For each AE reviewed, the CEC may also adjudicate its device-relatedness. Any analysis of the primary and secondary safety endpoints will be based on CEC-adjudicated data.

Specifically, the CEC will review:

- Any adverse events that are possibly, probably or definitely related to the MANTA device. The CEC members will adjudicate whether each event is a VARC-2 Major or Minor Femoral Vascular Complications within 30 days following procedure or whether it is no-event (does not meet either definition). determine the percentage of subjects with one or more VARC-2 Major or Minor Femoral Vascular Complications within 30 days following procedure.

The following events below will not be submitted for adjudication as these events do not meet the definitions of VARC-2 Major/Minor vascular complications or definitions in the MARVEL Protocol PSD-212.

- Hematoma: less than 2 cm in size or no size is recorded for the hematoma and it requires no treatment or requires only prolonged/adjunctive compression.

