## 5.2 Safety Endpoint 1: VARC-2 Major Complications

Objective: To quantify the real-world VARC-2 major femoral vascular complication incidence using the MANTA device.

Endpoint: The percentage of patients with one or more VARC-2 Major femoral vascular complications as adapted from VARC-2 definitions within 30 days following procedure. The classification of "major" will be determined by the CEC and will be recorded in the CEC spreadsheet.

VARC-2 Major femoral vascular complication definition:

- Femoral access site or access-related vascular injury (dissection, stenosis, perforation, rupture, arterio-venous fistula, pseudoaneurysm, hematoma, irreversible nerve injury, compartment syndrome, percutaneous closure device failure) leading to death, life-threatening or major bleeding; OR,
- downstream distal embolization (lower extremities) requiring surgery or resulting in amputation; OR,
- the use of unplanned endovascular or surgical intervention associated with death, major femoral bleeding; OR,
- any new ipsilateral lower extremity ischemia documented by patient symptoms, physical exam, and/or decreased or absent blood flow on lower extremity angiogram; OR,
- surgery for femoral access site-related nerve injury; OR,
- permanent femoral access site-related nerve injury.

Subjects to include: All subjects with a procedure attempt will be included in this analysis.

Statistical analysis (patient based): The number of subjects, percentage of patients and 95% confidence intervals for the percentage of subjects will be calculated at a minimum for subjects experiencing any type of major complication as previously defined. Additional summaries may include splitting into adverse event type as collected via the case report forms.

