## 5.3 Safety Endpoint 2: VARC-2 Minor Complication

Objective: To quantify the real-world VARC-2 minor femoral vascular complication incidence using the MANTA device.

Endpoint: The percentage of patients with one or more VARC-2 Minor femoral vascular complications (and no major VARC-2 complications) as adapted from VARC-2 definitions within 30 days following procedure.

Minor femoral vascular complication definition:

- Access site or access-related vascular injury (dissection, stenosis, perforation, rupture, arterio-venous fistula, pseudoaneuysms, hematomas, percutaneous closure device failure) not leading to death, life-threatening or major bleeding; OR,
- downstream distal embolization (lower extremities) treated with embolectomy and/or thrombectomy and not resulting in amputation; OR,
- any unplanned endovascular stenting or unplanned surgical intervention not meeting the criteria for a major vascular complication; OR,

- vascular repair or the need for vascular repair (via surgery, ultrasound guided compression, transcatheter embolization, or stent-graft); OR,
- percutaneous closure device failure\*.

\*Failure of a closure device to achieve hemostasis at the arteriotomy site leading to alternative treatment (other than manual compression or adjunctive endovascular ballooning).

Subjects to include: All subjects with a procedure attempt will be included in this analysis.

Statistical analysis (patient based): The number of subjects, percentage of patients and 95% confidence intervals for the percentage of subjects will be calculated at a minimum for subjects experiencing any type of minor complication as previously defined. Additional summaries may include splitting into adverse event type as collected via the case report forms.

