  2. Long-term MANTA AEs (Day 31-12M) will be summarized by seriousness for subjects that participated in the extended follow-up for the whole cohort, the 30 day cohort and the 12M cohort.
  3. Death summaries: any subjects that died will summarized by cause of death as adjudicated by CEC. Additionally, all AEs for those subjects will be listed.

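### CEC review is required only for AEs the investigator rates device-related, but the Major and Minor endpoints have no device condition and use only CEC-adjudicated data, so a qualifying access-related event can lack a required route to the endpoint

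*SAP*

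**What the plan says.** **Intake.** SAP section 3 states that "AEs that are considered by the investigator to be definitely, probably or possibly device related will be adjudicated by CEC parallel to enrollment" and repeats the criterion in its specific list of what the CEC reviews. Protocol 9.7 has the same rule. Protocol 9.5.1 is narrower and requires two conditions: "All AEs categorized by the Investigator as associated with MANTA leg and categorized by the Investigator as possibly, probably or definitely device-related". For everything else, "outcomes not associated with the MANTA device may also be adjudicated by CEC"; neither document says which outcomes are chosen.

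**Meaning of device-related.** Protocol 9.3 ties the term to the closure device and its deployment. It defines Not Related as "An AE which cannot be attributed to the MANTA device or initial study procedure".

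**Endpoints.** The first element of the Major definition in SAP 5.2 is "Femoral access site or access-related vascular injury" with a serious consequence. SAP 5.3 uses parallel wording for Minor, without that consequence. Major also includes new ischemia of the ipsilateral leg. None of these elements carries a device condition. SAP 5.3 restricts the Minor count to patients with a Minor event "and no major VARC-2 complications".

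**Data source.** SAP section 3 and Protocol 9.7 agree: "Any analysis of the primary and secondary safety endpoints will be based on CEC-adjudicated data". SAP 5.2 takes the Major classification from the CEC spreadsheet.

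**The concern.** The investigator's causality rating decides what the independent committee must see, yet causality is not part of the endpoint. Suppose a dissection is attributed to the procedural sheath, or a limb ischemia to underlying disease. Either may meet the definition and still not have to be referred. The committee cannot correct a rating on an event it never receives, and an event that is not adjudicated counts as no event.

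The Major rate is the primary safety endpoint of a registry meant to satisfy EU post-market follow-up requirements. SAP section 5 sets its 95% confidence interval beside pre-market and literature rates. Under Protocol 8.1 and 8.3.2 there is no hypothesis test and no comparative statistic, so no test decision is at risk. What is at risk is an understated complication rate in a safety report.

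**Working it through.** **1. The passages side by side**

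| Step | Condition on the event | Where |
|---|---|---|
| Mandatory CEC review | Investigator rates it possibly, probably or definitely device-related | SAP 3; Protocol 9.7 |
| Same, protocol reporting section | As above, and on the MANTA leg | Protocol 9.5.1 |
| Meets Major or Minor | Access-site or access-related injury (Major: also new ipsilateral ischemia); no device condition | SAP 5.2, 5.3; Protocol 4 |
| Counted in the endpoint | Adjudicated by the CEC | SAP 3, 5.2; Protocol 9.7 |

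The plan itself treats device and access site as different things. The last Minor element in Protocol 4 and SAP Appendix 1 lists device-related and access-site-related as alternatives. SAP 3 also has the CEC rate device relatedness and procedure relatedness separately.

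The fallback to the investigator's view when no CEC rating exists (SAP 5.6) is listed for the MedDRA tables of AEs and SAEs, not for the Major and Minor tables.

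**2. Direction of any error**

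- Major rate and any-complication rate: an unreferred qualifying event can only lower them.
- Minor-only rate: mainly lowered. A patient with a missed Major and a referred Minor would, however, be added to the Minor count, because SAP 5.3 excludes patients with a Major.

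**3. What the documents say about size**

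The plan states no figure that depends on the referral rule. The only evidence is the EU pre-market study summarised in the protocol introduction:

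- 17 femoral stenoses, all at one site: 2 possible + 15 definite = 17 rated device-related.
- 3 Major Complications: all rated probably or definitely device-related.
- Together 0 of 20 rated not related. Exact two-sided 95% upper limit: 1 − 0.025^(1/20) = 16.8%, if the events are treated as independent. The single-site clustering makes that doubtful.

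**4. Illustration under assumed loss**

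The loss shares below are assumptions; nothing in the documents supports a particular value. Intervals are exact (Clopper-Pearson); the SAP names no method. As a check on the method, 14/263 = 5.3% gives an upper 97.5% bound of 8.8%, as in SAP Table 2.

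Take N = 500 and a true Major rate equal to the 4.2% VARC-2 Major rate of the PMA trial (Table 2), so 0.042 × 500 = 21 events:

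| Assumed missed | Counted | Rate (95% CI) |
|---|---|---|
| 0 | 21 | 4.2% (2.6 to 6.4) |
| 2 (about 10%) | 19 | 3.8% (2.3 to 5.9) |
| 4 (about 20%) | 17 | 3.4% (2.0 to 5.4) |
| 6 (about 30%) | 15 | 3.0% (1.7 to 4.9) |

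The interval lies wholly below 4.2% only at 12 events or fewer: 12 gives 1.25 to 4.15%, and 13 gives 1.39 to 4.41%. Starting from 21, that means missing 9 (43%).

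Allowing for sampling variation, P(X ≤ 12) with X ~ Bin(500, 0.042 × (1 − loss)) is 2%, 6%, 14% and 29% at 0, 10, 20 and 30% loss.

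**The case against.** Three texts narrow the gap.

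- **Serious events.** SAP 3 and Protocol 9.7 make adjudicating SAEs a primary CEC responsibility, with no relatedness limit. Most Major elements (death, life-threatening or major bleeding, permanent injury) meet the protocol's SAE definition. In addition, SAP 5.6 has deaths "summarized by cause of death as adjudicated by CEC". This should catch most Major events. It is worded as a responsibility rather than a referral criterion, and it does not reach non-serious Minor events.
- **The Not Related category.** It also excludes anything attributable to the initial study procedure. If that means the index intervention, an injury from the sheath or puncture cannot be rated Not Related. The other three grades all trigger review, so it would be referred whether serious or not. This is the strongest point on the other side. It stands as one reading, but an ambiguous one, because Possible and Definite are worded around the device.
- **The charter.** The CEC works under a charter that is not among the documents and may already say which other outcomes are referred.

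Several stronger inferences are tempting, and the documents do not support them.

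- *Events were lost.* The texts show a gap in the rules, nothing more.
- *Loss falls mainly on non-serious Minor events.* The Not Related wording has no seriousness limit, so on the reading above those events are referred too.
- *The EU study's 29 hematomas and 46 not-related AEs bound the loss.* The hematoma ratings are not given, and only 5 of the hematomas were counted as Minor Complications, so those counts do not measure loss of qualifying events.
- *Events rated unknown drop out.* Unknown is missing from the intake rule and from the Protocol 9.3 scale. But SAP 5.6 treats it as related and plans a CEC determination in the listing that includes it. The passages need aligning; they do not show a loss.
- *Unsized hematomas withheld under SAP 3 are missed Minor complications.* They are not documented as meeting the protocol definition (over 2 cm, confirmed by ultrasound), so counting them would not correct the endpoint.

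**Conclusion.** The mismatch is real and visible in the text. Required referral depends on an investigator's device attribution that the endpoint definitions do not use, and only adjudicated events are counted. A qualifying access-related event not attributed to the closure device has no required route to the Major or Minor endpoint, and any such loss lowers the Major rate and the any-complication rate.

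The size is unknown and may be small. The SAE duty limits the likely effect on Major events, the Not Related wording may already route index-access injuries to review, and 0 of 20 rated access events in the EU study would have been missed. The loss table is an illustration at assumed shares, not an estimate. It shows that loss would have to be substantial before the descriptive comparison with 4.2% typically changed. The point is worth fixing because the remedy is specific and cheap, not because a bias has been shown.

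**What to change.** In SAP section 3, and in the CEC charter if it does not already say so, state that every AE at the MANTA access site or on the MANTA leg within the 30-day endpoint window goes to the existing CEC, whatever the investigator's causality rating, including not related and unknown. Report CEC device-related events as a subset of the Major and Minor counts. Align the treatment of unknown between SAP 3 and SAP 5.6. The existing clause allowing other outcomes to be adjudicated gives room for this.

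**Cost.** SAP and possibly charter wording, plus some extra adjudication. SAP section 5 says enrollment had closed and follow-up was still being completed when the plan was drafted, so part of the adjudication would be retrospective. The events can be selected, because Protocol 9.5.1 asks for unrelated AEs on the eCRF and has the investigator categorize association with the MANTA leg. Some source documents would have to be retrieved, since SAP 5.6 notes reduced data collection for AEs not related to MANTA. The number of added events cannot be judged from the documents, and the reported complication rate may be higher.

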The secondary performance endpoint Treatment Success was to evaluate the number of subjects that had Hemostasis Success and no Major Complications reported. Treatment Success was achieved in 47 subjects (94%). Absence of Hemostasis Success, as well as presence of one or more Major Complications, occurred in the same 3 subjects.

Safety Assessment

All adverse events (AEs) that were reported were assessed for type, severity, and device or procedure relatedness. In total, 101 AEs were reported during the course of the study, involving 45 subjects (90%). Forty-six (46, 45.5%) of these events were classified as 'not related' to the device. Of the 101 reported AEs, 25 were classified as 'serious'. Twenty-two (22, 88.0%) of these serious events were classified as 'not related' to the device. None of the AEs nor any of the SAEs were unanticipated.

The most common reported AE concerned a hematoma at the access site, which was reported 29 times (in 58% of the subjects) (10 times (20%) hematoma $>$ 6 cm; 19 times (38%) hematoma \leq 6 cm). One (1) of these hematomas was classified as 'moderate' severity, all others were classified as 'mild'.

Femoral artery stenosis was reported in 17 cases (34%). Although all events were reported as possible (2 cases, 4%) or definite (15 cases, 30%) related to the device, all events were classified as 'mild' severity and none of these femoral artery stenosis required intervention.

Twenty-five (25) AEs were classified as 'serious', involving 20 subjects (40%), of which 3 were probably or definitely device related (2 excessive access site bleedings; 1 pseudoaneurysm). All 3 events were classified as Major Complications.

During the course of the study, 4 subjects died. One (1) subject suffered from renal insufficiency and infection (cause unknown); another subject suffered from a cerebrovascular accident; 1 subject suffered from intestinal perforation; and the fourth subject suffered from a systemic infection. None of these events was considered related to the device nor to the procedure.

There were no unanticipated serious adverse device effects reported for any of the subjects.

Discussion

Safety

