  - Rationale: Per MARVEL Protocol PSD-212, a hematoma is defined as an expanding or non-expanding subcutaneous mass of blood greater than 2 cm in its longest axis, confirmed by ultrasound, and VARC-2 excludes percutaneous closure device failure requiring only manual compression from minor vascular complications.
- Minor Bleeding: requiring no treatment or requiring only prolonged/adjunctive compression.
  - Rationale: Per VACR-2 criteria, minor bleeding requiring adjunctive compression is not categorized as a VARC-2 major/minor vascular complication and percutaneous closure device failure requiring only manual compression is excluded from minor vascular complications.

The CEC member will provide the following assignments for each AE:

- If AE resulted in death, classify death:

- Cardiac
    - Non-cardiovascular
    - Vascular
  - If AE resulted in bleeding complications: (yes/no)
    - If yes, define event type below:
      - BARC 0
      - BARC 1
      - BARC 2
      - BARC 3a
      - BARC 3b
      - BARC 3c
      - BARC 4
      - BARC 5a
      - BARC 5b
  - VARC-2 Major Complication (yes/no)
    - Type of classification (from drop down list)
  - VARC-2 Minor Complication (yes/no)
    - Type of classification (from drop down list)
  - Device relatedness
    - Not related
    - Unknown
    - Possible
    - Probably
    - Definite
  - Procedure relatedness
    - Not related
    - Unknown
    - Possible
    - Probably
    - Definite

The CEC adjudications will be documented in a controlled limited access Excel spreadsheet.

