## 6 Data Conventions and Missing Data

No imputations will be made for missing data. All available data will be summarized for any summary provided the subject has a procedure attempt.

If an onset date for an AE is incomplete, every effort will be made by the clinical team to identify and collect a valid date from the site, but in case any are incomplete, then the following rules will be used:

- If the day of the month is missing, the first of the month will be used unless it precedes the procedure date. Then the procedure date will be used.
- If the month of missing the date of the procedure will be used.
- No year is expected to be missing as the follow-up is quite short.

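### SAP 3 withholds from the CEC hematomas of unrecorded size that were untreated or only compressed, so a missing measurement counts as no event and the Minor rate can only be understated

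*SAP*

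**What the plan says.** SAP 3 lists events that bypass the CEC: "The following events below will not be submitted for adjudication as these events do not meet the definitions of VARC-2 Major/Minor vascular complications". The hematoma entry covers those "less than 2 cm in size or no size is recorded for the hematoma and it requires no treatment", or needs only prolonged or adjunctive compression. The size condition and the treatment condition must both hold. An unsized hematoma that needed more than compression is not on the list.

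The stated rationale has two parts. One is the protocol definition: "a hematoma is defined as an expanding or non-expanding subcutaneous mass of blood greater than 2 cm in its longest axis, confirmed by ultrasound". The other is that VARC-2 does not count closure device failure managed by manual compression alone as a minor vascular complication.

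On the use of the adjudications, SAP 3 states: "Any analysis of the primary and secondary safety endpoints will be based on CEC-adjudicated data". SAP 5.3 defines Minor complications to include access-site injury such as "pseudoaneuysms, hematomas, percutaneous closure device failure) not leading to death, life-threatening or major bleeding; OR". It sets no treatment requirement for a hematoma, and its denominator is every subject with a procedure attempt.

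Protocol 9.5.1 and 9.7 provide for CEC review of events that the investigator rates possibly, probably or definitely device-related. Neither makes an exception for size or treatment.

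**The concern.** The rule treats two different states alike: a hematoma known to be small, and one that nobody measured. For the first, the 2 cm definition justifies the decision. For the second, the plan asserts that the definition is not met without the information needed to say so. An untreated 3 cm hematoma goes to the CEC if its size was written down and is dropped if the field was left blank.

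Since only adjudicated events can count and the subject stays in the denominator, incomplete recording can lower the reported Minor rate and can never raise it. Hematoma is a large part of this endpoint. In the EU pre-market study it was the most common adverse event, "which was reported 29 times (in 58% of the subjects", and Protocol 1.4 reports that all five Minor complications in that study were hematomas. SAP 5 then sets the 95% confidence interval against earlier rates, so a modest shift in the count can change what is reported.

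**Working it through.** The plan gives no figure that depends on this rule, and SAP 4 says the sample size has no statistical basis, so there is nothing to reproduce. The check has two parts.

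**1. Does the rationale cover an unrecorded size?**

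- *The 2 cm definition.* It supports excluding a recorded size below 2 cm. It gives no ground for classifying an unknown size.
- *The compression argument.* In SAP 5.3 and Protocol 4 the compression exception is a footnote to closure device failure. The hematoma element carries no such exception.
- *The protocol's referral rule.* Protocol 9.5.1 and 9.7 contain no exception, and SAP 3 itself restates the general rule before listing the exclusions.

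Neither part of the rationale reaches the unsized group.

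**2. How far could the Minor rate move?**

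Inputs from the documents: N = 500 (the planned maximum, SAP 4) and a comparison rate of 2.7% (U.S. pivotal trial, SAP Table 2).

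Inputs not in the documents: *u*, the number of subjects whose only candidate event is a withheld unsized hematoma, and *s*, the share of those that really exceeded 2 cm. Both are assumptions. The number wrongly dropped is k = u × s.

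Understatement = k / 500, so each subject wrongly dropped costs 1/500 = 0.2 percentage points. If s = 0, the understatement is zero.

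Suppose 14/500 = 2.8% are counted, close to the pivotal rate. Exact (Clopper-Pearson) intervals are used because the SAP names no method.

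| k restored | Minor rate | 95% CI | Covers 2.7%? |
|---|---|---|---|
| 0 | 14/500 = 2.8% | 1.5 to 4.7 | yes |
| 5 | 19/500 = 3.8% | 2.3 to 5.9 | yes |
| 8 | 22/500 = 4.4% | 2.8 to 6.6 | no |
| 10 | 24/500 = 4.8% | 3.1 to 7.1 | no |
| 25 | 39/500 = 7.8% | 5.6 to 10.5 | no |
| 50 | 64/500 = 12.8% | 10.0 to 16.0 | no |

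From this base, eight is the smallest number of restored subjects at which the interval excludes 2.7%. The SAP 5 statement that no difference has been demonstrated would then no longer apply.

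From a higher base the arithmetic is the same: 50/500 = 10.0% (7.5 to 13.0) becomes 75/500 = 15.0% (12.0 to 18.4) with 25 restored.

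**The case against.** The best defence is that the definition requires confirmation by ultrasound, so an unmeasured hematoma formally fails it. Two things weaken this. Neither schedule of assessments includes an ultrasound, so failing the test may only mean that nobody looked. And the SAP filter does not apply that test: a hematoma recorded at 2 cm or more is not excluded, whether or not ultrasound confirmed it.

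It is fair to add that this is a secondary endpoint in a descriptive single-arm registry with no hypothesis (Protocol 8.1). Protocol 7.8, 13.1 and 14.1 also provide in general terms for chasing missing data. That stands and limits the consequence. It does not settle how an event still unsized at the end is handled.

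A reader might infer more than the documents support:

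- *That no unsized hematoma ever reaches the CEC.* The rule covers only those untreated or merely compressed.
- *That the plan contradicts SAP 6.* SAP 6 says "No imputations will be made for missing data". SAP 3 fills in no size; it sets a threshold for referral. The effect resembles coding missing as no event, but that is an interpretation, not a textual conflict. The clearer conflict is with Protocol 9.5.1 and 9.7.
- *That the outputs would hide these events.* The adverse event tables and listings in SAP 5.6 would show them, with treatment and CEC determination. Size is not among the listed fields, so the unsized ones could not be picked out.

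**Conclusion.** The point holds in this form: for hematomas that were untreated or only compressed, an unrecorded size is counted as no Minor event, the stated rationale does not justify it, and the error can run only downward.

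The size is unknown. The firm statements are a floor of zero and 0.2 points per subject wrongly dropped at N = 500. The shift from 2.8% to 4.4% is an illustration that rests on an assumed base of 14 events and eight restored subjects.

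A reader might be tempted to derive a minimum loss of one or two points by applying the EU study's hematoma frequency and size mix to an assumed unsized share. The documents do not support that. Of the 10 EU reports above 6 cm, 5 were later confirmed as ecchymosis. Nothing shows that unsized, untreated hematomas have the same size mix as measured ones. SAP Table 2 gives the EU Minor rate as 0/50, where Protocol 1.4 gives 5/50.

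The change should be made, since it is cheap and the direction of the error is known.

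**What to change.** - Limit the hematoma exclusion in SAP 3 to those with a recorded size below 2 cm.
- Query the site for each hematoma with no size. The SAP was drafted with follow-up still under way, and SAP 6 already commits the team to recovering incomplete onset dates in the same manner.
- Send device-related hematomas still unsized to the CEC, as Protocol 9.5.1 and 9.7 provide, and report how many there were.
- Report the Minor rate twice, with unresolved unsized hematomas counted as no event and then as Minor.

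The cost is a few queries, a few more CEC cases and one sensitivity row. The Minor rate may rise.
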